### 9.3 POPULATION FOR ANALYSES

All enrolled subjects who are eligible based on the inclusion/exclusion criteria will be included in the population for analysis.

### 9.4 STATISTICAL ANALYSES

#### 9.4.1 GENERAL APPROACH

The planned statistical analyses will be included in a study Statistical Analysis Plan (SAP).

#### 9.4.2 ANALYSIS OF THE PRIMARY OBJECTIVE

Cox proportional hazards models will be fit to compare the risk of the primary endpoint based on platelet expression of FcγRIIa as a continuous variable. Subjects will be followed until their earliest MI, stroke, or death. Patients who do not experience the composite endpoint will be censored at their last telephone follow-up. Time to the primary endpoint will be calculated as days from study enrollment. Models will be adjusted for potential confounders including sex and other subject demographics and medical history collected at baseline. In the pilot study, it was observed that older age, diabetes mellitus, and prior revascularization were associated with higher platelet FcγRIIa expression.

A set of sensitivity analyses will evaluate FcγRIIa as a binary endpoint, which each analysis using a different threshold for classifying FcγRIIa as high or low. In particular, these analyses will explore whether a binary or a continuous measure of FcγRIIa provides greater predictive value, and whether or not a threshold of  $\geq 11,000/\text{platelet}$  is optimal.

#### 9.4.3 ANALYSIS OF THE SECONDARY OBJECTIVES

First Secondary Objective: Negative predictive value, positive predictive value, sensitivity, and specificity will be calculated. Prediction will be performed using a Cox regression model with the following predictors: platelet expression of FcγRIIa, sex, age, MVD, CKD, DM, and prior MI. Evaluation of the model's error rates will be based on a leave-one-out cross-validation approach. Additional models will evaluate the performance of the predictive model using a continuous measure of FcγRIIa with the performance of predictive models using various binary measures of FcγRIIa.

Second Secondary Objective: The adjusted Cox proportional hazards model described for the primary objective analysis will be used to compare the bleeding risk as a function of FcγRIIa expression, both as a continuous and as a binary variable.

#### 9.4.4 SAFETY ANALYSES

Not applicable as there is no study intervention.

#### 9.4.5 BASELINE DESCRIPTIVE STATISTICS

Descriptive statistics will be used to summarize clinical characteristics.

#### 9.4.6 SUB-GROUP ANALYSES

Not applicable.

#### 9.4.7 SUBSTUDY ANALYSES

Details on the substudy statistical analyses will be summarized in the SAP.

### 10 REGULATORY, ETHICAL, AND STUDY OVERSIGHT CONSIDERATIONS

#### 10.1 INFORMED CONSENT PROCESS

Prior to the start of the study and enrollment of any subjects, investigators must have the IRB's written approval for the protocol and the written informed consent form(s) and any other written information to be provided to the subjects.

Informed consent is a process that is initiated prior to the subject's agreeing to participate in the study and continues throughout the subject's study participation. The subject will be asked to read and review the informed consent document. The investigator will explain the study to the subject and answer any questions. The subject should have the opportunity to discuss the study with their family or surrogates or think about it prior to agreeing to participate. The subject will sign the informed consent document prior to any procedures being done specifically for the study. Subjects must be informed that participation is voluntary and that they may withdraw from the study at any time, without prejudice. A copy of the informed consent document will be given to the subject. The informed consent process will be conducted and documented in the source document (including the date), and the form signed, before the subject undergoes any study-specific procedures. The rights and welfare of the subjects will be protected by emphasizing to them that the quality of their medical care will not be adversely affected if they decline to participate in this study.

#### 10.2 STUDY DISCONTINUATION AND CLOSURE

This study may be temporarily suspended or prematurely terminated if there is sufficient reasonable cause. Written notification, documenting the reason for study suspension or termination, will be provided by the sponsor to investigators, study subjects and regulatory authorities. The study may resume if the cause of the temporary suspension has been sufficiently addressed to satisfy the sponsor, IRB and/or regulatory authorities.

### 10.3 CONFIDENTIALITY AND PRIVACY

Participant confidentiality and privacy is strictly held in trust by the participating investigators, their staff, and the sponsor(s) and their representatives. This confidentiality is extended to cover testing of blood samples in addition to the subject's clinical information. Therefore, the study protocol, documentation, data, and all other information generated will be held in strict confidence. No information concerning the study or the data will be released to any unauthorized third party without prior written approval of the sponsor.

The sponsor, other authorized representatives of the sponsor, representatives of the Institutional Review Board (IRB), or regulatory agencies may inspect all documents and records required to be maintained by the investigator, including but not limited to, medical records (office, clinic, or hospital). The clinical study site will permit access to such records upon request.

The subject's contact information will be securely stored at each clinical site for internal use during the study. At the end of the study, all records will continue to be kept in a secure location for as long a period as dictated by the reviewing IRB, Institutional policies, or sponsor requirements.

Study subject research data will be used for statistical analysis and scientific reporting, however this will not include the subject's contact or personal identifying information. Individual subjects and their research data will be identified by a unique study identification number.

After informed consent is obtained, each subject will be assigned a unique identifier. Clinical characteristics and biochemical results will be associated with the unique identifier. The association between the subject identity and the unique identifier will be kept in a secure file. Access to that information will be restricted to study personnel obtaining the information from the subject and key study personnel. Blood and derived specimens will be labeled with the unique identifier only.

Additionally, all study sites operate in full compliance with Health Insurance Portability and Accountability Act (HIPAA) regulations.

### 10.4 USE OF BLOOD SAMPLES

Blood samples taken for this study will be prepared, labeled, and shipped to the central laboratory for testing (see separate Laboratory Sample Manual for details). Blood, derived specimens, and biochemical results will be labeled and associated with the unique identifier only. Blood and derived specimens will be consumed during the assay process and any remaining samples will be appropriately destroyed at the end of the study. Samples will be assayed at a core laboratory and only study personnel will have access to the samples. After all assays have been completed and results confirmed, any remaining sample will be destroyed in accordance with the institutional biohazard disposal process. Samples will not be stored for use or testing beyond that described for this study. During the conduct of the study, an individual subject can choose to withdraw consent to have their blood sample tested, however, withdrawal of consent may not be possible after the sample has been tested.

## 10.6 CLINICAL MONITORING

Remote, centralized, and targeted data review will be conducted to ensure that the reported clinical data are accurate and complete, and that the conduct of the study is in compliance with the currently approved protocol/amendment(s). CRFs will be submitted periodically to the sponsor for review, database entry and endpoint event tracking. Source documents of endpoint events will be collected by the site and submitted for review by the sponsor. The investigator will confirm the endpoint event and there will be no adjudication by a separate committee.

## 10.7 QUALITY CONTROL

Quality control (QC) procedures will be implemented beginning with built in checks at data entry and in routine reports and QC checks that will be run on the database. Any missing data or data anomalies will be communicated to the site(s) for clarification/resolution.

## 10.8 DATA COLLECTION AND RECORD RETENTION

Data collection is the responsibility of the clinical trial staff at the site under the supervision of the site investigator. The investigator is responsible for ensuring the accuracy, completeness, legibility, and timeliness of the data reported. Source data will be captured in the subject's medical record, either electronic or hard copy in a neat, legible manner to ensure accurate interpretation of data.

Data recorded in the CRF derived from source documents should be consistent with the data recorded on the source documents. For subjects who experience an endpoint event, source documentation to confirm the event will be sent to the sponsor with any subject personal identifiable information redacted.

Sites will enter data directly into REDCap (Research Electronic Data Capture) Cloud, a secure web-based application designed to support data capture for research studies (Harris 2009). Data will be entered into an electronic CRF (eCRF) using REDCap Cloud and transmitted to the sponsor on a routine basis. REDCap Cloud databases are routinely backed-up and address the risk of storing sensitive clinical research data on the user's computer.

Study documents should be retained for a minimum of 2 years after the completion of the study. These documents should be retained for a longer period, however, if required by local regulations. No records will be destroyed without the written consent of the sponsor, if applicable.

#### 10.9 PROTOCOL DEVIATIONS

For this study, the only deviation to the protocol is if any of the inclusion are not met or if any of the exclusion criteria are met.

#### 10.10 PUBLICATION POLICY

There is a commitment to submit results of this study for publication within 18 months after database lock.

## 12 APPENDIX 1 – STUDY ENDPOINT EVENT DEFINITIONS

### Definition for Acute Myocardial Infarction (types 1, 2 and 3 MI) [Thygesen 2018]

The term acute myocardial infarction should be used when there is acute myocardial injury with clinical evidence of acute myocardial ischemia and with detection of a rise and/or fall of cTn values with at least 1 value above the 99th percentile URL and at least 1 of the following:

- Symptoms of myocardial ischemia;
- New ischemic ECG changes;
- Development of pathological Q waves;
- Imaging evidence of new loss of viable myocardium or new regional wall motion abnormality in a pattern consistent with an ischemic etiology;
- Identification of a coronary thrombus by angiography or autopsy (not for types 2 or 3 MIs).

Postmortem demonstration of acute atherothrombosis in the artery supplying the infarcted myocardium meets criteria for type 1 MI. Evidence of an imbalance between myocardial oxygen supply and demand unrelated to acute atherothrombosis meets criteria for type 2 MI. Cardiac death in patients with symptoms suggestive of myocardial ischemia and presumed new ischemic ECG changes before cTn values become available or abnormal meets criteria for type 3 MI.

### Definition for Stroke [Sacco 2013]

The term stroke should be used when there is focal ischemia within the perfusion territory of an artery that is stenosed or occluded, and cell death is localized to this region. In focal cerebral ischemia, cell death is maximal in the ischemic focus and may extend to the penumbra, with all cellular elements including both neurons and supportive cells affected. Clinical evidence of stroke includes both of the following:

- Symptoms of focal ischemia (e.g., unilateral weakness of an arm or leg) and
- Imaging evidence (CT or MRI) of CNS infarction

## Bleeding Academic Research Consortium (BARC) Definition for Bleeding [Mehran 2011]

Type 0: no bleeding

Type 1: bleeding that is not actionable and does not cause the patient to seek unscheduled performance of studies, hospitalization, or treatment by a healthcare professional; may include episodes leading to self-discontinuation of medical therapy by the patient without consulting a healthcare professional

Type 2: any overt, actionable sign of hemorrhage (eg, more bleeding than would be expected for a clinical circumstance, including bleeding found by imaging alone) that does not fit the criteria for type 3, 4, or 5 but does meet at least one of the following criteria: (1) requiring nonsurgical, medical intervention by a healthcare professional, (2) leading to hospitalization or increased level of care, or (3) prompting evaluation

Type 3:

Type 3a:

Overt bleeding plus hemoglobin drop of 3 to  $<5$  g/dL\* (provided hemoglobin drop is related to bleed)

Any transfusion with overt bleeding

Type 3b:

Overt bleeding plus hemoglobin drop  $\geq 5$  g/dL\* (provided hemoglobin drop is related to bleed)

Cardiac tamponade

Bleeding requiring surgical intervention for control (excluding dental/nasal/skin/hemorrhoid)

Bleeding requiring intravenous vasoactive agents

Type 3c:

Intracranial hemorrhage (does not include microbleeds or hemorrhagic transformation, does include intraspinal)

Subcategories confirmed by autopsy or imaging or lumbar puncture

Intraocular bleed compromising vision

Type 4: CABG-related bleeding

Perioperative intracranial bleeding within 48 h

Reoperation after closure of sternotomy for the purpose of controlling bleeding

Transfusion of  $\geq 5$  U whole blood or packed red blood cells within a 48-h period†

Chest tube output  $\geq 2$  L within a 24-h period

**Type 5: fatal bleeding**

**Type 5a:**

Probable fatal bleeding; no autopsy or imaging confirmation but clinically suspicious

**Type 5b:**

Definite fatal bleeding; overt bleeding or autopsy or imaging confirmation

Note: CABG indicates coronary artery bypass graft. Platelet transfusions should be recorded and reported but are not included in these definitions until further information is obtained about the relationship to outcomes. If a CABG-related bleed is not adjudicated as at least a type 3 severity event, it will be classified as not a bleeding event. If a bleeding event occurs with a clear temporal relationship to CABG (ie, within a 48-h time frame) but does not meet type 4 severity criteria, it will be classified as not a bleeding event.

\*Corrected for transfusion (1 U packed red blood cells or 1 U whole blood=1 g/dL hemoglobin).

†Cell saver products are not counted.

Abbreviations: CNS, central nervous system; CT, computed tomography; cTn, cardiac troponin; ECG, electrocardiogram; g/dL, grams/deciliter; h, hour; MI, myocardial infarction; MRI, magnetic resonance imaging; U, units; URL, upper reference limit.

5.1 Data Quality Assurance

All clinical entries in the eCRF will be stored in a RedCap Cloud database. The structure of the database is based on the division into sections and entry fields defined in the eCRF. To improve and ensure data quality, data checks will be performed automatically in the eCRF directly on electronic entry at the study site.

Plausible value ranges for numerical data entries and logical data and list entries will be filed in the eCRF. The tests for consistency and completeness based on this will be performed during entry in the eCRF. The validity of the recorded data will therefore be ensured by the validations incorporated in the documentation system, which highlight incorrect or implausible entries to the data entry clerk/doctor.

If corrections are necessary after the data are saved, these will be documented in an audit trail.

All tables, figures, and data listings to be included in the report will be independently checked for consistency, integrity and in accordance with standard procedures for analysis and reporting.

5.2 General Presentation Considerations

The Day 1 visit is the only in-person visit in this study. This will be followed by telephone visits every 6 months, and a final telephone visit after the required number of study endpoints have accrued and at least 18 months have elapsed after the last subject was enrolled.

Continuous data will be summarized in terms of the mean, standard deviation (SD), median, inter-quartile range, minimum, maximum and number of observations, unless otherwise stated. Continuous data exhibiting skewness may also be presented in terms of the maximum, upper quartile, median, lower quartile, minimum and number of observations. The minimum and maximum will be reported to the same number of decimal places as the raw data recorded in the database. The mean, median, lower quartile and upper quartile will be reported to one more decimal place than the raw data recorded in the database.

Categorical data will be summarized in terms of the number of subjects providing data at the relevant time point (n), frequency counts and percentages. The number of subjects with missing information for a specific variable will be displayed if applicable. Any collapsing of categories will be detailed in the data displays. Percentages will be presented to one decimal place. Percentages will be calculated using non-missing data as the denominator.

All report outputs will be produced using R version 4.3.0 or a later version.

5.3 Study Subjects

A clear accounting of the disposition of all subjects who enter the study will be provided, and a summary of the number and percentage of subjects by center will be produced.

A subject is considered to have completed the trial if the subject has adequate follow-up to assess all study outcomes through either the final study telephone visit or the date of death. For subjects who did not complete the trial two different dates are of interest: the last date for which information on nonfatal study outcomes is available and, if later, the date the subject died or was last known to be alive. The

latter can differ from the former when public records are used to determine vital status in a subject who is lost to follow-up.

Completeness of follow-up for the primary endpoint can therefore be assessed in multiple ways, and will be tabulated as follows:

1. Percentage of subjects with complete follow-up for all study outcomes through the final study telephone visit or the date of death
2. Percentage of subjects with complete follow-up for primary study outcomes through the final study visit or the occurrence of a primary study outcome,
3. Percentage of subjects with complete follow-up for vital status
4. Mean percentage of potential follow-up for primary study outcomes as defined in 2 above (defined as 100% for a subject with complete follow-up, or 100 times the number of days of complete follow-up divided by the number of days between the subject's Day 1 visit and the end of study for a subject with incomplete follow-up)
 - a. This percentage of follow-up will be subdivided into percentages of follow-up on DAPT and on monotherapy.
5. Mean percentage of potential follow-up for vital status as defined in 3 above (defined as 100% for a subject with complete follow-up or a subject who died, or 100 times the number of days of vital status follow-up divided by the number of days between the subject's Day 1 visit and the end of study for subjects with incomplete follow-up)

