## ABBREVIATIONS

ACS	Acute Coronary Syndrome
AE	Adverse Event
ASA	Acetylsalicylic Acid; Aspirin
BARC	Bleeding Academic Research Consortium
ARCTIC	Assessment by a Double Randomization of a Conventional Antiplatelet Strategy versus a Monitoring-guided Strategy for Drug-Eluting Stent Implantation and of Treatment Interruption versus Continuation One Year after Stenting
CFR	Code of Federal Regulations
CKD	Chronic Kidney Disease
CI	Confidence Interval
CRF	Case Report Form
CV	Coefficient of Variation
DAPT	Dual Antiplatelet Therapy
DM	Diabetes Mellitus
Fc	Fragment Constant
eCRF	Electronic Case Report Form
FcγRIIa	FcGammaRIIa
FDA	Food and Drug Administration
GCP	Good Clinical Practice
GFR	Glomerular Filtration Rate
GRAVITAS	Gauging Responsiveness with A VerifyNow assay-Impact on Thrombosis And Safety
HIPAA	Health Insurance Portability and Accountability Act
HR	Hazard Ratio
ICH	International Conference on Harmonisation
Ig	Immunoglobulin
IRB	Institutional Review Board
MI	Myocardial infarction
ml	milliliter
MVD	Multi-Vessel Coronary Artery Disease
ng	nanogram
nM	nanomolar
NSTEMI	Non-ST-segment elevation myocardial infarction
PCI	Percutaneous Coronary Intervention
QC	Quality Control
REDCap	Research Electronic Data Capture
REDUCE	Evaluation of short-term dual antiplatelet therapy in patients with acute coronary syndrome treated with a new-generation stent
SAE	Serious Adverse Event
SAP	Statistical Analysis Plan
SMART-DATE	6-month versus 12-month or longer dual antiplatelet therapy after percutaneous coronary intervention in patients with acute coronary syndrome
STEMI	ST-segment elevation myocardial infarction
SUSAR	Suspected Unexpected Serious Adverse Reaction
TIMI	Thrombolysis in Myocardial Infarction
TWILIGHT	Ticagrelor with or without Aspirin in High-Risk Patients after PCI
μg	microgram
U	Units
US	United States

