### **Prior study to evaluate FcγRIIa**

[name] et.al. completed a single center prospective trial designed to determine whether platelet expression of FcγRIIa would discriminate cardiovascular risk ([name] 2018). Patients (n=197) were enrolled shortly before discharge from a hospitalization for MI (both ST elevation and non-ST elevation were included). Although inclusion criteria allowed patients who

had been treated with PCI, coronary artery bypass grafting, or medically, all patients enrolled were treated with PCI. The primary endpoint, a composite of MI, stroke, death, and coronary revascularization, was lower in patients with platelet expression of FcγRIIa <11,000 (Figure 3). All patients were treated with ASA (81 mg) and treatment with clopidogrel (~64%) and ticagrelor (~36%) was balanced in patients with high and low platelet expression of FcγRIIa (Serrano 2007).

[figure not shown]

Figure 3: Summary of prospective single center study ([name] 2018)  
CVA=cerebrovascular accident, MI=myocardial infarction, Revasc=revascularization

Clinical characteristics of patients with high and low platelet expression of FcγRIIa were well balanced with the exception of older age, diabetes, and prior revascularization being more prominent in the high expression group. Cox multivariate analysis for the combination of MI, stroke, revascularization, and death demonstrated a hazard ratio of 3.0 ( $p=0.02$ ) for platelet expression of FcγRIIa  $>11,000$  when age, diabetes, and prior revascularization were included as covariates.

The incidence of revascularization was similar in patients with high and low platelet expression of FcγRIIa (low platelet FcγRIIa n=3, 3.2%; high platelet FcγRIIa n=4, 3.8%,  $p=0.815$ ). Patients with platelet expression of FcγRIIa  $\geq 11,000$  had a greater risk of MI, stroke, and death that became apparent after 6 months (Figure 4).

Cox regression analysis was performed and platelet expression of FcγRIIa was the sole covariate (hazard ratio 3.9,  $p=0.035$ ) associated with freedom from MI, stroke, and death.

[figure not shown]

Figure 4: Kaplan-Meier curves of the probability of freedom from MI, stroke, and death. The average duration of follow-up was 20 months (range 6-29 months).

MI=myocardial infarction

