## 4 STUDY DESIGN

### 4.1 OVERALL DESIGN

This is a prospective, observational multicenter non-interventional cohort study designed to integrate into the regular standard of care (Figure 5, Schematic Overview). Subjects who are admitted to the hospital with an MI will be screened. Screening will entail review of the medical

record for selected entry criteria. If the subject meets entry criteria, written informed consent will be obtained. Subjects will be enrolled into the study (called Day 1) before discharge from a hospitalization for a confirmed type 1 MI (STEMI or non-STEMI), referred to as the index event. Subjects will not have their care altered by participation in the study; subjects' medical regimens will be determined by their health care provider. Enrollment of subjects who are receiving anticoagulants for atrial fibrillation or venous thromboembolic disease will be limited to approximately 100 subjects.

[figure not shown]
After informed consent is obtained and the subject eligibility is confirmed, each subject will be assigned a unique identifier. Clinical characteristics and biochemical results will be associated with the unique identifier. The association between the subject's identity and the unique identifier will be kept in a secure file. Clinical characteristics will be recorded and blood (approximately 3 ml to 6 ml) will be obtained for analysis of platelet FcγRIIa expression. Blood can be taken up to 2 weeks post-study enrollment. The samples for platelet FcγRIIa expression will be assayed by a core laboratory to ensure standardization.

Subjects will be contacted by telephone every 6 months and asked a standardized set of questions to determine whether they have had a cardiovascular event (MI, stroke), bleeding event or have died. At each study visit, subjects will be queried about their medications with a specific focus on their anti-thrombotic regimen. Changes to their anti-thrombotic regimen will be documented in association with the time when changes were made. All subjects will be contacted at the end of the study for a final telephone visit. Medical records will be reviewed to confirm subject reported endpoints.

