The primary endpoint will be the composite of death, MI, and stroke. MI will be defined in accordance with the 4th universal definition (Thygesen 2018) and stroke consistent with consensus guidelines (Sacco 2013). The incidence of clinically significant bleeding will be determined using the Bleeding Academic Research Consortium (BARC) scale (Mehran 2011) and is defined as BARC type 2-5. Study endpoint events will be confirmed by the review of medical records by the investigator and all relevant medical records will be obtained by the site for submission to the sponsor (as described in Section 10.8). Subjects who experience an endpoint event will continue to be followed throughout the entire study and any subsequent endpoint events will also be confirmed and recorded. See Appendix 1 for study endpoint event definitions.

A total of approximately 800 subjects will be enrolled at approximately 10-20 sites in the US. It is anticipated that it will take about 12 months to enroll the total number of subjects. The study and subject follow-up will continue until 1) at least 80 ischemic events (MI, stroke, and death) have occurred, and 2) the last subject enrolled has completed at least 18 months of follow-up. Based on an annual ischemic event rate of 10%, the overall length of participation in the study is anticipated to be up to 3 years. Results will be monitored during the course of the study.

Figure 5 Schematic Overview of the Study

MI=myocardial infarction; NSTEMI= non-ST-segment elevation MI, STEMI= ST-segment elevation MI

\* Subjects who experience an endpoint event will continue to be followed throughout the entire study and any subsequent events will also be confirmed and recorded.

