5.7 Statistical Methods

5.7.1 Analysis of the Primary Objective

The primary analysis of the primary endpoint will be a Cox proportional hazards model. The dependent variable is the number of days from enrolment to the occurrence of a primary endpoint, with censoring at the last day of complete follow-up; independent variables will be FcγRIIa (measured in thousands), age in years, history of diabetes mellitus, prior revascularization, multi-vessel coronary artery disease (MVD) defined as ≥2 vessels or left main with a stenosis ≥50%, chronic kidney disease (CKD) defined as estimated glomerular filtration rate (GFR) < 60 ml/min/1.73 m², prior MI, hypertension, tobacco use, heart failure or LVEF<30%, previous stroke or transient ischemic attack, and peripheral arterial disease. Interest is in the FcγRIIa parameter: point estimate (increase in risk per 1000-unit increase in FcγRIIa), confidence interval and p-value. FcγRIIa will be declared to be associated with cardiovascular risk if the 2-sided p-value from this model is < 0.05.

A set of exploratory/sensitivity and subgroup analyses based on the Cox model will also be conducted.

- Instead of censoring at the last day of complete follow-up, censor at the last day of vital status follow-up
- FcγRIIa as the only covariate in the model
- Separate analyses of each component of the primary endpoint: MI and stroke, both censored at the last day of complete follow-up, and death, censored at the last day of vital status follow-up
- Run the primary model in subgroups defined by age (in decades), sex, history of diabetes and prior revascularization (including all covariates except the subgroup variable in the model)
- Run the primary model with the use of DAPT (any use prior to a primary endpoint), and its interaction with FcγRIIa, as additional covariates

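### The SAP's antithrombotic classes leave out anticoagulants, although up to about 100 of 800 subjects may be taking one, so the exploratory FcγRIIa-by-DAPT model mixes DAPT use with anticoagulation

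*SAP*

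**What the plan says.** **Who is enrolled.** Protocol 4.1 states: "Enrollment of subjects who are receiving anticoagulants for atrial fibrillation or venous thromboembolic disease will be limited to approximately 100 subjects". On size it states: "A total of approximately 800 subjects will be enrolled at approximately 10-20 sites in the US". Protocol 5.2 has no anticoagulant exclusion; the revision history records that version 4.0 removed it.

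**How follow-up is divided.** SAP 5.3 lists measures of completeness of follow-up. Under item 4, the mean percentage of potential follow-up for the primary outcome, sub-item 4a says: "This percentage of follow-up will be subdivided into percentages of follow-up on DAPT and on monotherapy". It names two classes. DAPT appears in the protocol's abbreviations only as "Dual Antiplatelet Therapy", and monotherapy is not defined.

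**How DAPT enters the model.** SAP 5.7.1 introduces its secondary Cox analyses with: "A set of exploratory/sensitivity and subgroup analyses based on the Cox model will also be conducted". One of them is: "Run the primary model with the use of DAPT (any use prior to a primary endpoint), and its interaction with FcγRIIa, as additional covariates". The primary model's covariate list ends with "hypertension, tobacco use, heart failure or LVEF<30%, previous stroke or transient ischemic attack, and peripheral arterial disease". Anticoagulant use, atrial fibrillation and venous thromboembolism appear nowhere in that list, and the SAP has no anticoagulant subgroup or sensitivity analysis.

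**What is recorded.** Protocol 1.3 schedules an antithrombotic medication review on Day 1 and at every telephone visit. Protocol 4.1 has regimen changes recorded with their timing.

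**The concern.** Item 4a divides a total, so every day of follow-up needs a class. For an anticoagulated subject the SAP gives no rule, and different programmers could score the same day differently.

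In the interaction model, a subject never on DAPT is coded no, whether on one antiplatelet, an anticoagulant, both, or nothing. An anticoagulated subject with even brief DAPT use is coded yes. Anticoagulated subjects can thus sit on both sides of the contrast, and the reasons for anticoagulation (atrial fibrillation, venous thromboembolism) are not adjusted for. A DAPT main effect or FcγRIIa-by-DAPT interaction could then partly reflect anticoagulation or its indication, and a reader could not tell.

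This matters because Protocol 2.3 (Current Study) expects preliminary evidence on the prognostic meaning of FcγRIIa under different antithrombotic regimens, to support a later trial. The DAPT interaction is the only model in the SAP that addresses regimen.

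**Working it through.** The plan gives no figure for the make-up of the no-DAPT group, so there is none to reproduce.

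**Inputs from the documents**
- Cap on anticoagulated subjects: about 100 (Protocol 4.1).
- Planned enrolment: about 800 (Protocol 4.1).
- Event target: at least 80 (SAP 5.10), that is 80/800 = 10% of subjects.

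**Assumptions (not in the documents)**
- p = share of anticoagulated subjects who never take DAPT before an endpoint or censoring.
- q = the same share among the other subjects.

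**Step 1: size of the unclassified part.** 100/800 = 12.5% of subjects. If the cap is filled and these subjects spend all follow-up on an anticoagulant plus one antiplatelet, the item 4a monotherapy figure could move by up to 12.5 percentage points on the scoring choice alone. This bound needs neither p nor q.

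**Step 2: make-up of the never-DAPT group.** With the cap filled, the anticoagulated share is 100p / (100p + 700q). Example: p = 0.5 and q = 5% give 50/(50 + 35) = 59%. Shares, with group size in brackets:

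| p | q = 2% | q = 5% | q = 10% | q = 20% |
|---|---|---|---|---|
| 1.0 | 88% (114) | 74% (135) | 59% (170) | 42% (240) |
| 0.5 | 78% (64) | 59% (85) | 42% (120) | 26% (190) |
| 0.25 | 64% (39) | 42% (60) | 26% (95) | 15% (165) |
| 0.1 | 42% (24) | 22% (45) | 12% (80) | 7% (150) |

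At p = 0.1 and q = 30% the share is 10/220, about 5%.

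**Step 3: when they are a majority.** 100p > 700q means q < p/7: below 14.3% at p = 1, 7.1% at p = 0.5, 3.6% at p = 0.25 and 1.4% at p = 0.1. If only 50 anticoagulated subjects are enrolled, 50p > 750q means q < p/15, or 3.3% at p = 0.5.

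**Step 4: events in the never-DAPT group.** If the 10% event proportion applies throughout, the group holds 0.10 × (100p + 700q) events. Over the table this runs from 0.10 × 24, about 2, to 0.10 × 240 = 24, out of 80. Without the anticoagulated subjects it is 0.10 × 700q: about 2 events at q = 3% (21 subjects) and 3.5 at q = 5% (35 subjects).

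**Step 5: model size.** Counting one parameter per variable, the primary model has 12 (FcγRIIa and 11 others). DAPT and its interaction make 14; one anticoagulant term makes 15. Four regimen classes with interactions would instead add 3 + 3 = 6, making 18. At 80 events that is 80/14 = 5.7, 80/15 = 5.3 and 80/18 = 4.4 events per parameter.

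**The case against.** **Not every anticoagulant regimen is unplaced.** A reader might infer that no anticoagulant regimen fits the two classes. The documents do not support that. DAPT plus an anticoagulant is still DAPT, and any such use makes the subject DAPT = yes in 5.7.1. Protocol 2.1 uses monotherapy for a single antiplatelet drug, so an anticoagulant plus one antiplatelet could be read as monotherapy. What stands: an anticoagulant alone and no therapy have no class, and the combination with one antiplatelet has no rule.

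**A mainly anticoagulated no-DAPT group is not established.** A reader might also infer that the no-DAPT group will consist largely of anticoagulated subjects. That needs q < p/7, and neither share is given. The pilot makes a low q plausible: "All patients were treated with ASA (81 mg) and treatment with clopidogrel (~64%) and ticagrelor (~36%) was balanced". But all pilot patients had PCI, whereas the present criteria do not require it and treatment is left to the provider (Protocol 6), so q may be higher. The cap may also not be reached.

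**Little formally depends on it.** Item 4a is a descriptive line and the DAPT model is exploratory. The SAP does not say that the model estimates DAPT against monotherapy. All of this stands, and it limits the weight of the point without supplying the missing rule.

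**Larger remedies would be unsound.** Four regimen classes with interactions would give 18 parameters for about 80 events. The classes also divide time rather than subjects, so they cannot simply replace an any-use covariate. A fit restricted to non-anticoagulated subjects, used alone, could rest on a handful of never-DAPT events. Both criticisms are accepted in the fix.

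**Conclusion.** The gap is real but minor. The item 4a split is not exhaustive for a cohort in which up to 12.5% may be anticoagulated at enrolment, and the DAPT terms in 5.7.1 are mixed with anticoagulation and its indication. That much follows from the text.

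How strong the mixing is cannot be derived. For p from 0.1 to 1 and q from 2% to 30%, with the cap filled, the anticoagulated share of the never-DAPT group runs from about 5% to 88%. With few never-DAPT events, the interaction would also be imprecise.

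The primary test of FcγRIIa uses neither the follow-up split nor the DAPT term and is unaffected. What is at risk is the interpretation of the one regimen model.

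**What to change.** **SAP 5.3 item 4a.** Divide follow-up into four classes: DAPT without anticoagulant, single antiplatelet without anticoagulant, any anticoagulant-containing regimen, and none. Because the classes apply to time, they also capture anticoagulants started after enrolment.

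**SAP 5.7.1, DAPT model.** Keep the model and make three additions:
1. Baseline anticoagulant use (yes/no) as one covariate.
2. A cross-tabulation of subjects and primary events by DAPT use and anticoagulant use, so that the make-up of the no-DAPT group is visible.
3. A repeat of the FcγRIIa-by-DAPT interaction, as a sensitivity analysis, in subjects not on an anticoagulant at baseline. The single covariate adjusts the level of risk but does not separate the two regimens within the interaction; the restricted fit addresses that.

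**Cost.** A few lines of SAP text and modest programming, with no new data. The model gains one parameter (14 to 15, or 5.7 to 5.3 events per parameter at 80 events). The restricted fit loses up to about 12.5% of subjects and may be imprecise because few never-DAPT subjects and events remain, so it should be reported as supportive only. The text should be settled before results are seen.
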